The **central hypothesis** of this study is that rTMS therapy in PCD can potentiate the effects of BoNT injections. With the current standard treatment, the peak-dose benefits seen with BoNT are seen at about 4-6 weeks after the administration of injections. We plan to introduce a 1 week course of rTMS around 2-8 weeks before or after BoNT or T1). We may examine the effects of combined therapy at around 10 weeks after BoNT (T2) and at around12 weeks after BoNT (T3) injections follow-up (Figure A). We will record the clinical outcome with the Toronto Western Spasmodic Torticollis Rating Scale (TWSTRS), a standardized validated rating scale for PCD. We will also measure the physiological effects at these time points with transcranial magnetic stimulation (TMS) technique, a useful tool to understand the brain physiology. We will measure the effects of rTMS on cerebellar excitability with a well-established TMS parameter referred to as cerebellar inhibition (CBI). As mentioned in aforementioned section, rTMS delivered at 1 Hz and below inhibits the brain

4/20/2015

and when delivered at frequencies greater than 5 Hz, ^{7,11-13} it excites the brain. Based on previous imaging studies that showed increased activation of cerebellum in dystonia, ^{16-21,28} we plan to use low frequency rTMS to achieve inhibition of cerebellum and improvement of symptoms.

It is reasonable to be concerned that the alongside the effects of low frequency rTMS on excitatory loops, the inhibitory loops in the cerebellum could as well be further inhibited by rTMS. We are therefore planning to include the cerebello-cortical inhibition circuit to determine the effects of rTMS on an inhibitory loop.

[figure not shown]
SPECIFIC AIM 1: Clinical impact of rTMS therapy in PCD.

[figure not shown]
We will determine the clinical effects of 1-Hz rTMS therapy of the cerebellum when combined with BoNT injections in PCD. Comparisons will be drawn in the clinical scoring of TWSTRS (blinded videotape ratings) between T1 (around 6 weeks after BoNT injections or the start of rTMS therapy), T2 (around 10 weeks after) and T3 (around 12 weeks after or at the time of next BoNT injection) assessments. We hypothesize benefits seen at T2 follow-up compared to T1 will be greater in the group receiving combined rTMS and BoNT therapy compared with standard BoNT alone. Similar effects will be seen at T3 follow-up but they will be reduced in magnitude. (Figure C)

[figure not shown]

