Eligible subjects will be invited to an introductory session. We will obtain IRB approved informed consent. Subjects will be explained in detail about the procedures outlined for the study. Subjects will have a detailed medical history and neurological examination using the NINDS Common Data Elements. Subjects will be randomized to receive BoNT therapy combined with real or sham rTMS (1:1, 10 subjects in each arm). At our center, PCD subjects are scheduled for BoNT injections approximately every 12 weeks. rTMS therapy will be administered in the period around 2-8 weeks before or after the BoNT injections. Although the physician administering TMS will be aware of the status of the subject in terms of real TMS versus sham-TMS, this physician will play no role in any of the outcome measures, and will not be present during any of the outcome measure assessments. Similarly, the investigator who performs the outcome measures will not be present during any of the TMS sessions, and therefore will remain blinded to the status of the patients with respect to real rTMS versus sham rTMS.

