Data Safety Monitoring Plan

The principal investigator monitors the patient safety and data collection of each study visit. If she feels there is possible harm to subject safety or the possibility of, any harm due to something new that was learned during the study, she will convene a multi-disciplinary committee of at least 2 health professionals to perform a thorough review of the study details.

Regulatory Approval, Statistics, Time Line

The study will be approved by the University of Florida Institutional Review Board, and all subjects will provide informed consent. The study is highly feasible given the large number of PCD subjects seen at UF and the considerable expertise. Statistical analyses will be performed using commercially available statistical software (SPSS, version 19.0; SPSS, Inc., Chicago, Illinois). We aim to enroll 20 subjects for this pilot study, and 10 control subjects. For Aim1 and 2a, we will conduct a mixed model analysis using time and stimulation arm as repeated factors adjusted for baseline values, and subjects as the random factor. The model will include 2 factors: treatment (2 levels: real vs sham) and time (3 levels: T1, T1, and T3). The 2-tailed significance level will be set at 0.05 For Aim 2b, we will use Spearman correlation test to determine the relation between the change in CBI at T2 compared to that at T1 and change in CBI at T3 compared to that at T1. With an expected difference of 30% in TWSTRS scores at 10 weeks between the two arms (real and sham rTMS), a standard deviation of 20%, type I error of 5% and power of 80%, the necessary sample size for each group is ten completers.

TIME AND EVENTS TABLE

Description	Screenin g	rTM S V1	rTM S V2	rTMS V3	rTMS V4	rTMS V5	10 wk FU*	12wk FU*
Consent	Х							
Neurological Exam	Х							
Med History	Х							
Inclusion/Excl.	Х							
Botox Injection (SOC)	X							
Randomization	x							
MRI		Х				Х		
rTMS (real/shame)		Х	Х	Х	Х	Х		
Determine Threshold	X							
Videotape		Х				Х	х	Х
Blinded Rater Eval		Х				Х	х	Х
Urine pregnancy	x							
CDQ 24	Х					Х	Х	Х
Clinical Assessments								
TWSTRS		Х				Х	Х	X

Physiological Tests						
CBI measured with TMS	X			Х	Х	Х

*optional

References:

1. Fahn S (Ed): Movement disorders 2. London: Buttersworth; 1987.

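### The injection that starts the clock for T2 and T3 is not named while rTMS may come before or after BoNT, so the interval from rTMS to T2 can be anywhere from 0 to 18 weeks

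*Combined protocol and SAP*

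**What the plan says.** All references are to the combined protocol and SAP.

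- **Order of treatments.** STUDY DESIGN: "rTMS therapy will be administered in the period around 2-8 weeks before or after the BoNT injections". The central-hypothesis paragraph adds a further anchor: "We plan to introduce a 1 week course of rTMS around 2-8 weeks before or after BoNT or T1".
- **T1.** SPECIFIC AIM 1: "T1 (around 6 weeks after BoNT injections or the start of rTMS therapy".
- **T2 and T3.** The central-hypothesis paragraph places them at "around 10 weeks after BoNT (T2) and at around12 weeks after BoNT (T3) injections follow-up". SPECIFIC AIM 1 names no anchor for T2 and gives the last assessment as "T3 (around 12 weeks after or at the time of next BoNT injection".
- **Cycle length.** STUDY DESIGN: "At our center, PCD subjects are scheduled for BoNT injections approximately every 12 weeks".
- **Schedule.** In the TIME AND EVENTS TABLE, the row "Botox Injection (SOC)" is marked only at Screening, ahead of the five rTMS visits. The 10- and 12-week follow-ups are marked optional and have no stated time zero.
- **Use of T2.** Aim 1 hypothesises a larger T1-to-T2 benefit with real rTMS. The sample size rests on a 30% TWSTRS difference at 10 weeks.

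**The concern.** Injections recur about every 12 weeks, so *after BoNT* identifies a date only if the injection is named. When rTMS may fall on either side of an injection, two subjects can both follow the plan and yet have T2 at very different distances from rTMS, one with a further BoNT injection in between and one without.

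The baseline moves as well. If T1 is the start of rTMS, it can fall anywhere from week 2 to week 10 of a cycle. The plan itself puts peak BoNT benefit at about 4-6 weeks and enrols only subjects whose benefit lasts 10 weeks or less, so the T1-to-T2 change expected without any rTMS effect depends on when rTMS was given.

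At stake is whether the contrast that carries Aim 1 and the sample size measures one quantity, and whether 20 subjects suffice to detect it.

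**Working it through.** **1. The plan's sample size.** Inputs (Regulatory Approval, Statistics, Time Line): difference 30, SD 20, two-sided 5%, power 80%. The standardised difference is 30/20 = 1.5.
- Normal approximation: 2 × (1.960 + 0.842)² / 1.5² = 6.98, so 7 per group.
- Two-sample t-test: 8.06, so 9 per group. Power at 10 per group is 0.887.

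The stated ten completers is adequate on its own inputs, with a small margin.

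**2. rTMS start to T2, on a 12-week cycle, T2 at week 10 from the index injection.**

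| Reading | rTMS start, weeks from index | rTMS start to T2 | BoNT between rTMS and T2 |
|---|---|---|---|
| A. rTMS after the index injection | 2 to 8 | 10−8 = 2 to 10−2 = 8 weeks | No |
| B. rTMS before the next injection, preceding one counted | 12−8 = 4 to 12−2 = 10 | 10−10 = 0 to 10−4 = 6 weeks | No |
| C. rTMS before an injection, that following one counted | −8 to −2 | 10+2 = 12 to 10+8 = 18 weeks | Yes, 2-8 weeks after rTMS starts |

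The readings overlap. rTMS at weeks 4-8 of a cycle is both after one injection and before the next, so one subject can have T2 at week 10 or at week 10 + 12 = 22.

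**3. The extremes.**
- B with rTMS at week 10: T2 coincides with the first session. If T1 is the start of rTMS, T1 and T2 are the same date and the change is empty.
- C: T2 is 12-18 weeks after the start of a one-week course, or 11-17 weeks after its end. The only persistence figure the plan cites is 12 weeks, after an eight-week course in another disease.
- T1 at week 6 with rTMS at week 2: T1 comes 6−2 = 4 weeks after rTMS starts and is not a baseline. The events table puts the first TWSTRS at the first rTMS visit, which favours the other anchor, but the text leaves both.

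**4. Dilution.** Suppose a share f of real-arm subjects is timed so that T2 holds no rTMS effect. The documents do not give f, so a range is shown. The mean difference becomes 30 × (1−f). The SD is held at 20, which leaves out the extra spread from mixed timings.

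| f | Difference | Power, 10 per arm |
|---|---|---|
| 0 | 30 | 0.89 |
| 0.1 | 27 | 0.81 |
| 0.2 | 24 | 0.72 |
| 0.3 | 21 | 0.60 |
| 0.5 | 15 | 0.36 |

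Ten per arm gives 80% power for a difference of 26.5, so power drops below 80% once f exceeds 1 − 26.5/30 = 0.12, between one and two of the ten real-arm subjects. With the difference kept at 30, the largest SD that still gives 80% power is about 22.6, so there is also little room for added variance.

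**5. Chance imbalance in order.** Assume 10 of 20 subjects have rTMS before BoNT. With 10 per arm:
- P(5:5) = C(10,5)² / C(20,10) = 63,504 / 184,756 = 0.344
- P(6:4 either way) = 2 × 44,100 / 184,756 = 0.477
- P(7:3 or worse) = 1 − 0.344 − 0.477 = 0.179

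If order shifted the T1-to-T2 change by an assumed 10-20 points, a 7:3 split would move the arm difference by (0.7−0.3) × 10 to 20 = 4 to 8 points. The standard error of the arm difference is 20 × √(2/10) = 8.9 points.

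**The case against.** The strongest reply is that one reading fits every section. Take the Screening injection in the events table as the index for everyone, and read *before* as before the next scheduled injection. rTMS then falls at weeks 2-10, T2 at week 10 and T3 at week 12, with no injection in between. The timeline figure, which is not available here, may show exactly this. The reading is plausible, but no sentence states it, and it still leaves 0 to 8 weeks between rTMS and T2.

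Second, allocation is randomised against sham and both arms receive BoNT. The hypothesis is that rTMS potentiates BoNT, so a BoNT response after rTMS is within what the study tests. This stands: mixed timing does not in itself favour either arm. It does not answer the dilution or the variance.

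Third, this is a pilot, and the figures for dilution and imbalance rest on assumed shares and order effects. That also stands. The week arithmetic rests on the plan's own figures.

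A reader might infer more than the documents support:
- **That some subjects will be re-injected between rTMS and T2.** This is permitted under reading C only.
- **That T3 can precede T2.** Counted from a single injection, week 12 always follows week 10. The reversal needs T3's alternative definition, the next injection, combined with a different anchor for T2.
- **That the 4-8 points are bias.** They are chance imbalance with expectation zero, below one standard error, and a 7:3 or worse split is avoided about 82% of the time.
- **That the unblinded physician could choose the order by arm.** The plan says this physician gives the stimulation and has no role in outcomes. It does not say who schedules rTMS.

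**Conclusion.** The point holds as a conflict in the timing rules. Followed as written, the plan allows 0 to 18 weeks between the start of rTMS and T2, with or without an intervening BoNT injection, and two definitions of T1. This affects the time point that carries Aim 1 and the sample size, so it is more than a missing detail.

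The consequence is loss of a single meaning for the contrast, dilution and added variance. On the plan's own SD, power falls below 80% once about 12% of real-arm subjects have no rTMS effect at T2. That share is an assumption. The chance of a 7:3 or worse split in order is 0.18 if half the subjects are treated before BoNT, also an assumption.

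No systematic bias between arms is shown, provided order is independent of arm, and the stated ten per group is not in error. The intervals assume cycles of exactly 12 weeks, where the plan says approximately.

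**What to change.** Reconcile the central-hypothesis paragraph, SPECIFIC AIM 1, STUDY DESIGN and the TIME AND EVENTS TABLE. Which order of rTMS and BoNT is right is for the investigators, and this review takes no position on it.

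- Name one index injection per subject as time zero. Give T1, T2 and T3 one definition each from it, with T2 always before T3, and print time zero in the events table.
- Record the index injection and the planned dates for each subject before the allocation is released.
- If both orders are kept, fix each subject's order before randomisation. Include order, or the rTMS-to-T2 interval, in the mixed model. If T1 remains one of the repeated time levels, let that term vary with time so that it acts on the T1-to-T2 change. Stratify the 1:1 list by order if that is feasible with 20 subjects.

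Modelling order deals with imbalance and variance but does not restore a diluted effect, so the single time zero is the essential part. The cost is protocol wording, a model term and slightly less flexible scheduling, with no extra visits or subjects.

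### The Aim 1 model does not target the 10-week comparison that Aim 1 and the sample size name: arm is called a repeated factor, no T2 contrast is stated, and baseline is not identified

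*Combined protocol and SAP*

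**What the plan says.** All references are to the combined protocol and SAP.

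- **Design** (STUDY DESIGN): "Subjects will be randomized to receive BoNT therapy combined with real or sham rTMS (1:1, 10 subjects in each arm". This is a parallel-group trial with one arm per subject.
- **Hypothesis** (SPECIFIC AIM 1): "We hypothesize benefits seen at T2 follow-up compared to T1 will be greater in the group receiving combined rTMS and BoNT therapy", compared with BoNT alone. For the later visit: "Similar effects will be seen at T3 follow-up but they will be reduced in magnitude".
- **Model** (Regulatory Approval, Statistics, Time Line): a "mixed model analysis using time and stimulation arm as repeated factors adjusted for baseline values, and subjects as the random factor". The two factors are "treatment (2 levels: real vs sham) and time (3 levels: T1, T1, and T3". The text gives no arm-by-time term, no contrast at a named visit, and no visit that serves as baseline.
- **Sample size** (same section): "With an expected difference of 30% in TWSTRS scores at 10 weeks between the two arms (real and sham rTMS", with SD 20%, 5% type I error and 80% power, leading to ten completers per group.
- **Timing:** SPECIFIC AIM 1 defines "T1 (around 6 weeks after BoNT injections or the start of rTMS therapy". STUDY DESIGN says "rTMS therapy will be administered in the period around 2-8 weeks before or after the BoNT injections". In the TIME AND EVENTS TABLE the first TWSTRS is at rTMS V1, none is marked at screening, and the 10- and 12-week visits are optional.

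**The concern.** The hypothesis and the sample size both point to T2. The model text does not. Read literally, a model with a treatment factor and a time factor yields one arm effect, averaged over the visits in the outcome. If T1 is the pre-stimulation visit, that average includes a visit at which no treatment effect can exist.

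Three different tests fit the text: the arm main effect, the arm difference at T2, and the arm difference in T2 minus T1. They estimate different things, and nothing fixes the choice before the data are seen. The unnamed baseline adds to this. The events table suggests that it is T1, but that is an inference, and T1 would then stand on both sides of the model.

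At stake is whether the reported result answers the question that the trial was sized for.

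**Working it through.** **Inputs.** From the plan: difference 30, SD 20, two-sided 0.05, 10 per arm, a T3 effect smaller than at T2. Assumed, because the plan does not say: 30 and 20 are on one scale, 20 is a single-visit SD, visits are equally correlated at r = 0.3, 0.5 or 0.7, and data are complete.

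**1. The plan's own figure.** For a two-sample t test at one visit, the noncentrality is 30 / (20 × √(2/n)). At n = 10 this is 30/8.94 = 3.35. Power is 79.7% at n = 8, 84.8% at n = 9 and 88.7% at n = 10. The exact t test therefore needs 9 per arm (the normal approximation gives 7), and ten is slightly conservative. The figure reproduces as a single-visit comparison at T2.

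**2. What the averaged arm effect estimates.** With visit effects d1, d2 and d3, the arm main effect is (d1 + d2 + d3)/3. If T1 precedes stimulation, d1 = 0.
- T3 effect half of T2: (0 + 30 + 15)/3 = 15.
- T3 effect fully sustained: (0 + 30 + 30)/3 = 20.

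These values do not depend on the SD or the correlation. Adjusting for T1 does not change them, because the arms have the same expected T1.

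**3. Why power is nevertheless kept.** Given T1, the three-visit mean varies only through T2 and T3. Its variance is [2 × 400(1 − r²) + 2 × 400 r(1 − r)]/9 = 800(1 − r)(1 + 2r)/9. At r = 0.5 this is 88.9, so the SD is 9.43 and the SE of the arm difference is about 9.43 × √0.2 = 4.22. The ratio is 15/4.22 = 3.56. For T2 alone adjusted for T1, the SD is 20√(1 − 0.25) = 17.3, the SE is 7.75 and the ratio is 30/7.75 = 3.87. The estimate is halved, but its standard error falls nearly as much.

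Simulated power (40,000 trials per setting, T2 effect 30):

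| Test | r = 0.3 | r = 0.5 | r = 0.7 |
|---|---|---|---|
| Arm main effect, T1 as covariate, T3 effect 15 | 86% | 90% | 97% |
| Arm main effect, T1 as covariate, T3 effect 30 | 98% | 99% | 99.9% |
| ANCOVA of T2 on T1 | 89% | 94% | 99% |

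If 20 is instead the SD of change, the single-visit SD is 20/√(2(1 − r)) = 16.9, 20.0 or 25.8. At a T3 effect of 15, the averaged test then has 95%, 90% and 84%, and the T2 ANCOVA has 97%, 94% and 91%. All of these exceed the planned 80%.

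**4. Baseline and T1.** The first TWSTRS in the events table is at V1, which matches the second definition of T1 (start of rTMS). Under the first definition (about 6 weeks after BoNT), a course given before BoNT, or 2 to 5 weeks after it, would begin before T1. The definitions agree only for some of the permitted schedules.

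**The case against.** The strongest reply is that the text lists factors, not model terms. A two-factor analysis commonly includes the interaction, and the T2 target appears both in Aim 1 and in the sample size paragraph. On that view only a linking sentence is missing, in a trial that calls itself a pilot. Part of this stands: an interaction is not excluded, so the dilution is conditional on reporting the main effect. But the linking sentence is what decides which estimate is the trial's result.

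Several stronger readings are tempting, and the documents do not support them.

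- **Lost power.** Without baseline adjustment, the averaged test at a T3 effect of 15 would have only 58%, 49% or 43% power at r = 0.3, 0.5 or 0.7. The plan states that it adjusts for baseline, so these figures do not describe it. With T1 as covariate, power falls well below 80% only if the effect has vanished at T3, whereas Aim 1 expects a reduced effect.
- **Inflated false-positive rate.** A rate of about 9% to 10% arises if T1 is both covariate and outcome in a common random-intercept model, an interaction is added, and the arm difference at T2 alone is tested. That is a chain of assumed readings. In the same model the contrast closest to Aim 1's wording, T2 minus T1, rejects at 4.9% to 5.5%.
- **T1 after stimulation.** Adjusting for such a T1 would remove part of the effect. The definitions permit this, but the events table points the other way and the documents give no size for an effect at T1. It is a scheduling inconsistency to reconcile, not a demonstrated bias.
- **T2 dropped, or a crossover implied.** The repeated T1 is almost certainly a misprint for T2. No numerical harm is shown from calling arm repeated.

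**Conclusion.** Wrong as written, and worth correcting before analysis. The text misdescribes the randomised arm, omits T2 from the time levels, leaves baseline unidentified while T1 is also an outcome level, and names no test of the 10-week difference.

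The gap in the text is certain. The size of the harm is conditional: if the arm main effect is reported and T1 is the pre-rTMS visit, a 30-point effect at 10 weeks appears as 15 to 20, for a T3 effect between half and all of that at T2. The main harm is an estimate that does not answer the 10-week question, not a loss of planned power. A reader might infer that the sample size is faulty. It is not shown to be: ten per arm reproduces with a small margin for a T2 comparison, and the mismatch lies in the model text.

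**What to change.** In the statistics section:

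1. State that arm is a between-subject fixed factor and time the only repeated factor.
2. Define baseline as the TWSTRS taken before the first rTMS session (V1 in the events table), and use it as a covariate only, not as an outcome level.
3. Name the real-minus-sham difference at T2 as the main test at two-sided 0.05, with T3 secondary. Use ANCOVA of T2 on baseline, or the equivalent T2 contrast from a model of T2 and T3 with an arm-by-time term (equivalent when the baseline slope and the variance may differ by visit).
4. Correct the list of time levels so that T2 appears.
5. Reconcile the two definitions of T1 in SPECIFIC AIM 1, and the rTMS timing in STUDY DESIGN, with the events table.

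The cost is wording only, with the same data and software. There are two downsides. If the effect is fully sustained at T3, the T2 test has slightly less power than the averaged test (about 94% against 99% at r = 0.5). It also depends on the 10-week visit, which the table marks optional: at r = 0.3, 0.5 and 0.7, power is 80%, 87% and 96% with 8 completers per arm, and 63%, 72% and 87% with 6.

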Title: Combined therapy with rTMS and botulinum toxin in primary cervical dystonia

Principal Investigator: [name] [name]

Sub-Investigator: [name]

Primary cervical dystonia (PCD) is the most common form of focal dystonia.¹ PCD is frequently reported as a source of disability,² decreased quality of life,³ and social stigma.⁴ Botulinum toxin (BoNT) is the gold standard treatment for PCD (Class I evidence, Level A recommendations).⁴ This therapy has the advantage of avoiding central side effects such as sedation, cognitive clouding, and balance impairment, which are risks related to oral pharmacotherapy such as anticholinergic medications. Although the current standard of care is injecting no more frequently than every 12 weeks to reduce the risk of developing immunity, patients commonly report fading of benefits sooner than 12 weeks following the injection.⁵ We conducted a retrospective analysis of PCD patients injected with BoNT at our center (n=150). We found the average duration of benefits from BoNT injections was about 9.5 weeks which was also reported by other studies.⁵ Also, BoNT treatment is known to provide only pure symptomatic benefits and does not seem to modify the disease pathophysiology.^{3,4,6} Thus although BoNT therapy is the first-line approach for treatment of PCD, in many patients it provides only suboptimal benefits. Therefore there is clearly a merit in exploring other options to potentiate and possibly prolong the benefits of BoNT therapy.

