Outcome measures. The clinical outcome will be measured with Toronto Western Spasmodic Torticollis Rating Scale (TWSTRS). The TWSTRS is a widely accepted composite rating scale for PCD with subscales for clinical severity, functional disability, and associated pain. Studies evaluating the clinimetric properties of TWSTRS have demonstrated substantial reliability, validity, and responsiveness to change following therapeutic intervention. It is the most commonly employed outcome measure in PCD trials and has practical applicability in a clinical setting. Also, we will administer the Craniocervical Dystonia Questionnaire Description for quality of life assessment. The Craniocervical Dystonia Questionnaire (CDQ-24) is a patient-rated health related quality of life (HR-QoL) measure for craniocervical Dystonia on 5 HR-QoL domains. It is composed of 24 items, forming 5 subscales: stigma, emotional well-being, pain, activities of daily living, and social/ family life. Items are rated on a 5-point scale.²³ Each item consists of five statements representing increasing severity of impairment, scored from 0 to 4. Subjects will be instructed to indicate how they have felt during the past two weeks because of dystonia by selecting one of the five statements for each item. Subjects will also rate their symptoms before and after stimulation using a 7-point nominal scale: 1) excellent, 2) very good, 3) good, 4) average, 5) slightly worse than usual, 6) bad or 7) very bad.

We will record videos of subjects at T1, and possibly at T2 and T3 time points which will be scored by two independent blinded raters (excluding control patients). We will obtain IRB approval to consent subjects in order to obtain videos of all subjects (excluding control subjects). The physiological outcome will be measured with TMS (CBI measure). We will also obtain MRI scan before and after rTMS therapy.

Brain Structure Measures: We will be using the research dedicated 3T Phillips or 3T Siemens MRI scanners in the McKnight Brain Institute to obtain diffusion tensor imaging, T1 weighted, and T2 weighted images. ²¹ We will be using the 32 channel head coil (Phillips) or 64 channel head coil (Siemens) for data acquisition.

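### The V5 rating at the end of the rTMS course is scheduled, and is the only post-rTMS rating not marked optional, but no stated analysis uses it

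*Combined protocol and SAP*

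**What the plan says.** **Schedule.** The Time and Events Table marks TWSTRS, videotape and the row "Blinded Rater Eval" at V1, V5, the 10-week follow-up and the 12-week follow-up. A footnote makes the 10- and 12-week visits optional. The CBI row has four marks, but its column alignment is lost in the text available, so a CBI measurement at V5 cannot be confirmed.

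**Time points.** Specific Aim 1 defines "T1 (around 6 weeks after BoNT injections or the start of rTMS therapy", which places T1 at V1. The central-hypothesis paragraph places the later assessments "at around 10 weeks after BoNT (T2) and at around12 weeks after BoNT (T3) injections follow-up". V5 has no T-label.

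**Analysis.** For Aims 1 and 2a the statistics section specifies a baseline-adjusted mixed model: "The model will include 2 factors: treatment (2 levels: real vs sham) and time (3 levels: T1, T1, and T3". The Aim 1 hypothesis is "We hypothesize benefits seen at T2 follow-up compared to T1 will be greater in the group receiving combined rTMS and BoNT therapy". Aim 2b and the sample-size statement also refer only to T1, T2 or T3.

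**Text on videos.** The outcome-measures section says "We will record videos of subjects at T1, and possibly at T2 and T3 time points" and does not mention V5.

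**The concern.** The stated model excludes a blinded rating that the schedule requires, and it depends for all its post-treatment information on two visits that patients may skip. There are two consequences.

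- A patient without the 10- and 12-week visits adds nothing after baseline to Aim 1, even if rated blind at V5. The sample size asks for ten completers per arm and exactly ten per arm are to be randomized, so there is no reserve.
- With T1, T2 and T3 alone, the trial cannot separate a one-week course that does nothing from one that works and then fades. For a pilot these point to different next studies. The protocol's example of benefit lasting 12 weeks comes from eight weeks of rTMS in Parkinson's disease, so persistence after one week is an open question.

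If V5 is first analysed after unblinding, the result will be post hoc.

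**Working it through.** **1. Reproduce the planned sample size.** Inputs from the statistics section: difference 30, SD 20, two-sided 0.05, power 80%.

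- Normal approximation: n = 2 × (1.96 + 0.84)² × 20² / 30² = 6.98, so 7 per arm.
- Two-sample t-test (noncentral t): 9 per arm.
- With the planned 10 per arm: noncentrality 30 / (20 × √(2/10)) = 3.35 on 18 degrees of freedom, power 88.7%.

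The stated 10 is slightly conservative. It concerns the 10-week visit only.

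**2. Count the ratings left out.** Four scheduled ratings × 20 patients = 80, of which V5 is 20. Post-rTMS ratings (V5, T2, T3) are 3 × 20 = 60, of which V5 is 20, or one third.

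**3. Locate V5.** With T1 at week 6 and a one-week course, V5 falls at about week 7, and the gap to T2 is 10 − 7 = 3 weeks. With rTMS starting 2 to 8 weeks after BoNT, V5 falls at weeks 3 to 9 and the gap is 7 to 1 weeks. For rTMS given before the injection, the documents do not fix the gap.

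**4. Power at T2 if the effect fades.** Assumption: a true difference of 30 at V5 decays exponentially, so the difference at T2 is 30 × 0.5^(gap / half-life). Same t-test, 10 per arm, SD 20. The documents give no decay rate, hence the range.

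| Half-life (weeks) | Difference at T2, 3-week gap | Power at T2 |
|---|---|---|
| 1 | 3.8 | 7% |
| 2 | 10.6 | 20% |
| 3 | 15.0 | 36% |
| 6 | 21.2 | 61% |
| 12 | 25.2 | 76% |

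With a 3-week half-life, power is 71% for a 1-week gap and 10% for a 7-week gap.

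**5. The effect is gone by T2.** Take a difference of 30 at V5 and zero at T2 and T3. A joint between-arm test on T2 and T3 rejects 5% of the time, by construction. For a joint test on k visits, the noncentrality is λ = (n/2) d′S⁻¹d, referred to F with k and 2n − k − 1 degrees of freedom. With V5 added, k = 3 and λ is 13.1, 16.9 or 26.6 for between-visit correlations of 0.3, 0.5 or 0.7 (assumed). Power is then 77%, 87.5% or 98%. A V5 contrast alone has 88.7% power at 0.05, or 80.9% at 0.025.

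**6. Optional visits.** For a full difference of 30 at T2, power falls from 89% with 10 per arm to 80% with 8, 73% with 7 and 55% with 5.

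**7. Cost of adding V5 to a joint test.** Take true differences of 30 at T2 and 20 at T3, with correlation 0.5. The joint test on T2 and T3 has λ = 11.67 and power 80%. Adding V5 gives 72% if the V5 difference is 15 and 83% if it is 30. Adding a level can therefore weaken a joint test.

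**8. Multiplicity.** Testing V5 and T2 each at 0.05 gives a familywise error of 1 − 0.95² = 9.75% if the tests are independent.

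**The case against.** The strongest defence is that T2 is the study question. The trial aims to prolong benefit in patients whose BoNT effect lasts 10 weeks or less, so testing at week 10 is deliberate and a null result there answers Aim 1. This stands, and T2 should remain the main time point. Nothing prevents descriptive reporting of V5 either, but that does not give V5 a prespecified role.

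Four stronger readings are tempting, and the documents do not support them.

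- *A reader might infer that BoNT wear-off contaminates T2 and that V5 is nearly free of it.* The protocol does say "the peak-dose benefits seen with BoNT are seen at about 4-6 weeks after the administration of injections" and "We found the average duration of benefits from BoNT injections was about 9.5 weeks". But both randomized arms receive BoNT, so wear-off common to both does not bias real versus sham. Nor is V5 always early: with rTMS starting 8 weeks after BoNT it falls near week 9, and the protocol also allows rTMS before the injection.
- *A reader might infer that V5 is where the largest effect is expected.* No hypothesis is stated for V5. Aims 1 and 2a place the effect at T2, with less at T3.
- *A reader might infer that a short-lived effect would be reported as no effect.* The chance rate applies only if the effect is gone by T2. A partly retained effect is under-detected, to the degree shown in the table.
- *A reader might take the repeated T1 label as a sign that V5 was meant.* It is more simply a slip for T2.

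Two practical objections also stand. The outcome-measures text does not name V5 among the video times, so blinded rating at V5 is not yet secure. And adding a time level is not neutral if the test is a joint one (step 7).

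**Conclusion.** The point holds as a gap in the analysis plan: V5 is scheduled for blinded rating, is the only post-rTMS rating not marked optional, and has no stated analysis. One third of scheduled post-rTMS ratings (20 of 60) is unused.

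On the nominal 3-week gap, power at T2 for an effect of 30 at V5 is 7% to 76% over half-lives of 1 to 12 weeks, and 5% if nothing remains. A V5 contrast would have 88.7% power with the planned 10 per arm. These figures rest on the protocol's SD of 20, on applying its difference of 30 to V5, and on assumed decay rates and correlations. The omission itself rests on none of them.

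This is not a claim that the T2 comparison is biased or that T2 is the wrong primary time point. The change should be made before unblinding.

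**What to change.** 1. Correct the repeated T1 label to T2 and give V5 a defined time label.
2. Reconcile the outcome-measures text on videos with the Time and Events Table, so that V5 is clearly filmed and rated blind.
3. Reconcile the differing statements of rTMS timing relative to BoNT, so that V5 and its gap to T2 have a defined position.
4. Use V1 as the baseline covariate and V5, T2 and T3 as the post-baseline time levels for TWSTRS, and for CBI if it is measured at V5. V1 is then not both a covariate and a time level. Patients without T2 or T3 still contribute their V5 value.
5. Name the real-sham difference at T2 as the primary contrast at two-sided 0.05, in place of a joint interaction test.
6. Name the real-sham difference at V5 as a secondary contrast, either interpreted as supportive or tested only after T2. If testing is to follow T2, note that a null result at T2 leaves V5 descriptive.

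The cost is a few sentences in the statistics and outcome-measures sections. If V5 is filmed and rated as the table shows, no visit, rating or patient is added, and the sample size need not change. The downside is one more secondary comparison, whose place in the testing order must be stated.
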